## **Study design and participants**

We prospectively enrolled children 24 months and younger and pregnant women from a rural community in the Mewat region located within the state of Haryana, India from July 11, 2016 to July 20, 2017. Recruitment and follow up were performed concurrently, though the recruitment target was met on February 11, 2017. The study was administered by Bal Umang Drishya Sanstha (BUDS), a New Delhi based non-profit organization with a focus on child health. This study was approved by the Research Ethics Committees of BUDS, New Delhi, India and the Johns Hopkins University, Baltimore, MD, USA. This trial is registered with ClinicalTrials.gov, number NCT03180138.

## **Study Procedures**

An encrypted, cloud-based software platform developed by Royal Datamatics Pvt Ltd (RDPL), New Delhi, India was used for record keeping and delivery of automated mobile-phone reminders and compliance-linked incentives (Supplementary Figure 1). Any child 24 months or younger at the time of enrollment, with a mobile-phone in the household and the ability of their caregiver to provide written informed consent were considered eligible for this study. After obtaining written informed consent from the caregiver, basic demographic information, Global Positioning System (GPS)-location and caregiver's finger biometrics were collected. While the standard of care in this setting involves the use of written immunization records (cards and records at the local primary health center) and verbal notification of follow up visits, record keeping for all groups in this study, including the control group, was performed using the software platform. Eligible subjects were randomly assigned to one of three study groups: self-returns with software platform for record keeping (control), automated mobile-phone reminders alone, and automated reminders with compliance-linked incentives in the form of mobile-phone talk-time. At the time of enrollment, data on prior immunizations received by the child were obtained from government-issued immunization cards provided by the families. If cards were unavailable or lost, immunization records were verified using written records at the local primary health center. The government-run National Immunization program (Supplementary Table 1) provided and administered the immunizations. The date for the next scheduled immunization visit was provided at each follow up by the government staff and entered into the software platform by the field workers. Each follow up visit was also correlated with the scheduled return date (if recorded in the system) of the administered immunization. Since finger identification is unreliable in young children, the child's name along with their caregiver's fingerprint was used to ensure positive identification of individual children at every visit. The GPS coordinates (longitude and latitude) were also recorded at recruitment and at each follow up visit. All users (field staff and study team) were identified and logged onto the software platform using biometric identification. For the study groups receiving automated reminders, Short Message Service (SMS) in the local language (Hindi) were sent. At follow up visits, mobile-phone minutes equivalent to INR 30 (~USD 0.5) per completed immunization were provided in the compliance-linked incentives group. The amount of incentive was determined after input from the local investigators as well as the community workers. All data transfers and compliance-linked incentives transactions were automated and occurred in real-time.

## **Randomization and masking**

Randomization was stratified by group (young children or pregnant) using a block randomization algorithm (block size of six), but in the current manuscript, only data for children is presented. All caregivers were informed of their child's group assignment and study field staff had access to group assignments for individual patients at the time of recruitment or follow up visits; however, all other study team members were blinded to the group assignments until the end of the study and after analysis of the blinded groups.

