## Statistical Analysis Plan

*Sample size:* Prior to the study, we anticipated that our best intervention would increase the baseline immunization coverage by least 20% compared to the control group. Assuming up to a 20% exclusion rate, we calculated that a sample of size 175 per group would yield us 90% power at 5% level of significance for this outcome.

*Statistical analysis:* Baseline data across the three study groups was summarized using either median and interquartile range (IQR) or frequencies and percentages. Multivariable Poisson regression analysis was used to estimate adjusted immunization rates in the two test study groups with the control group as reference. To compare immunization coverage at enrollment and at the end of the study, the incidence rate ratio was calculated accounting for median patient days in the study and the number of subjects for each intervention group. Unadjusted immunization coverage for each study group was calculated with Poisson exact 95% confidence intervals. Multivariable Poisson regression analysis was used to estimate adjusted immunization rates in the two test study groups with the control group as reference. Comparison between groups for timeliness of immunization was calculated using the Fisher-exact test. Data analysis was performed using Stata Version 14 (StataCorp LLC, College Station, TX USA) or GraphPad Prism Version 6.05 (La Jolla, CA 92037 USA).

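### One stated block size of six, recruiters who see assignments and no described concealment make children's allocations partly predictable, with at most one in five certain in advance

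*Combined protocol and SAP*

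**What the plan says.** Three places in the combined protocol and SAP bear on this point.

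- **Randomization and masking.** Children were allocated "using a block randomization algorithm (block size of six"; no other size is mentioned. The only stratifier is the type of participant: "Randomization was stratified by group (young children or pregnant". No stratum for site or field worker is described, so the children appear to share one sequence. Caregivers were told which arm their child was in. As for those who recruited, "study field staff had access to group assignments for individual patients at the time of recruitment or follow up visits". The rest of the team was masked: "all other study team members were blinded to the group assignments until the end of the study".
- **Study Procedures.** "Eligible subjects were randomly assigned to one of three study groups". The narrative puts consent, demographics, location and fingerprints before assignment, and the retrieval of prior immunization records after it. It does not say whether that order is chronological.
- **Statistical Analysis Plan, sample size.** The target is "a sample of size 175 per group". The allocation ratio is not written out.

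The documents do not say who or what held the sequence, whether the block size was withheld from field staff, or whether the arm was released only after registration could no longer be undone.

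**The concern.** When blocks are small and equal in size, past assignments carry information about the next one. Consent before assignment does not remove this, because a recruiter who can foresee the next arm can choose whom to approach, or when to register a family, before asking for consent.

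Several features of this trial make that matter. Eligibility is broad, and no consecutive-enrolment rule or screening log is described. Field staff are locally recruited (End Points section, paragraph on authentication). In the incentive arm, talk-time is delivered to the phone at enrolment and checked by the field worker, so that assignment is conspicuous. The primary outcome, immunization coverage, depends on families coming back, which a local worker might be able to judge beforehand.

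If families more likely to return were placed in the incentive arm, its comparison with control would be biased from the start. The SAP specifies multivariable Poisson regression but names no covariates, so adjustment cannot be relied on to remove such a bias.

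**Working it through.** The plan gives no figure for predictability, so there is none to reproduce.

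**Inputs.** Block size 6 (Randomization and masking). Three arms (Study Procedures). Two places per arm per block, from the 1:1:1 ratio inferred from 175 per group. Total 3 × 175 = 525, taking that target to refer to the children. The number of recruiters is not given, so I use one, two and three.

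**1. Certain allocations, one observer of the whole sequence.** There are 6!/(2!·2!·2!) = 90 equally likely orderings. An allocation is certain when only one arm has places left.
- Places 1 to 4: never, because four places must be used up first.
- Place 5: certain if the last two places belong to the same arm, probability 1/5.
- Place 6: always.

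Share = (0 + 0 + 0 + 0 + 1/5 + 1)/6 = 1.2/6 = 20.0%, or 0.20 × 525 = 105 children.

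**2. Best guess, same observer.** The chance that the best guess is right at places 1 to 6 is 1/3, 2/5, 1/2, 8/15, 3/5 and 1. The sum is 3.367, and 3.367/6 = 56.1%, against 33.3% by chance.

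**3. The incentive arm alone.** It is known to be next for 20.0%/3 = 6.7% of allocations. It is known to be impossible when both its places are used: (0 + 0 + 1 + 3 + 6 + 10)/15 = 1.333 per block, and 1.333/6 = 22.2%.

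**4. Several recruiters, each seeing only their own enrolments.** Assume children fall to k recruiters at random and, generously, that block boundaries are known. Certainty then requires that the recruiter also enrolled all four children who took the other two arms' places, probability (1/k)⁴. The share is 0.20/k⁴:
- k = 2: 0.20/16 = 1.25%
- k = 3: 0.20/81 = 0.25%

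For the best guess at place i, the number of earlier children this recruiter has seen in the block is binomial(i − 1, 1/k). With m seen, the hit rate is the step 2 value for place m + 1. Averaging over the six places gives 42.6% for k = 2 and 39.4% for k = 3.

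**5. Alternatives, one observer of the whole sequence.**
- Unrestricted randomisation: 0% certain, 33.3% guessed. SD of an arm's size = √(525 × 1/3 × 2/3) = 10.8. The average increase in the variance of a between-arm comparison is about (10.8/175)² = 0.4%.
- Random blocks of 6, 9 and 12, observer knows the set of sizes: about 2.6% certain and 53% guessed, by simulation.

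| Design and observer | Certain | Best guess |
|---|---|---|
| Block of six, whole sequence seen | 20.0% | 56% |
| Block of six, two recruiters, own enrolments only | 1.25% | 43% |
| Block of six, three recruiters, own enrolments only | 0.25% | 39% |
| Blocks of 6, 9 and 12, whole sequence seen | about 2.6% | 53% |
| Unrestricted | 0% | 33% |

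**The case against.** The strongest reply is that the 20% describes an observer the documents do not establish. They refer to field workers in the plural, and the access they grant is to assignments of individual patients, which is not the same as a view of the running list. They do not say that staff knew the block size. A reader might infer that one in five allocations was in fact known in advance. The text does not support that; 20% is the top of a range. This part of the objection stands. It does not remove the concern, because the documents equally do not rule out a view of all assignments, in which case the figure remains 20%.

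A second reply is that varying the block size achieves little, since the best guess falls only from 56% to 53% and steering does not need certainty. This also stands, and it is why unrestricted randomisation is the better remedy. It would be wrong to add that the present design with two recruiters (1.25% certain) already beats mixed blocks (about 2.6%): the second figure is for an observer of the whole sequence, so the two are not like for like.

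Third, motive is conjectural. The reward is small (INR 20 at enrolment, then INR 30 per immunization) and goes to caregivers. A reader might infer that families were steered to the incentive arm. Nothing in the documents shows that.

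Finally, part of the remedy is nearly in place: coverage is measured at enrolment, and baseline data are summarised for the three groups. The account of concealment is still missing.

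**Conclusion.** The point holds as a weakness of design and description. One stated block size of six, field staff who see assignments at recruitment, and no described concealment leave the next allocation partly predictable. The certain share lies between about 0.25% and 20% over the cases examined, and the best guess between 39% and 56%. Where in that range the trial fell depends on how many recruiters shared the sequence and what the platform showed them, neither of which is stated.

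The figures assume a 1:1:1 ratio, a single children's sequence, a block size that did not vary, and block boundaries known to the recruiter. The last makes them upper values for each case. The size of any resulting bias cannot be calculated, because it depends on how far steered families would differ in their tendency to return. Silence about concealment is not evidence that there was none.

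**What to change.** **As a design.** In Randomization and masking, replace the fixed block of six with unrestricted randomisation by the software platform. Suggested wording: *The platform allocates each child to one of the three groups with equal probability, independently of earlier allocations. It displays the group only after consent and all enrolment data, including prior immunizations, have been entered and locked.* A smaller gain comes from randomly varying blocks, for example 6, 9 and 12, with the sizes withheld from field staff; the same rule on when the arm is shown should apply.

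The cost is a software setting, a sentence or two of text and a slightly larger chance imbalance. Under unrestricted randomisation, two SDs around 175 is 175 ± 2 × 10.8, or roughly 153 to 197 per arm, with an average loss of precision under 1%.

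**For this trial.** The Study design and participants section describes the recruitment target as met, so the allocation method can no longer be changed. The sponsor should state how many field workers enrolled children, whether they could view assignments other than their own, whether they knew the block size, and whether prior immunizations were recorded before the arm was shown. Enrolment coverage should be compared by arm. That check is partial: it would not reveal steering on a trait unrelated to past immunization, and it is weaker if prior immunizations were recorded after the arm was known.

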## **End Points**

Immunization coverage was the primary outcome of the study and was calculated for each child as the proportion of the total number of immunizations received divided by the total number of immunizations required at the time of measurement (i.e. at enrollment, end of study, etc.). We also calculated the cost in mobile-phone messaging and compliance-linked incentives. Timeliness of immunizations was a secondary outcome measure and was defined as the proportion of immunizations administered before or within 14 days after the scheduled date recorded during the study.

*Authentication and follow up:* The field staff were locally recruited and trained prior to the study. A pilot run of the software platform was performed at the study site in May-June 2016 to assess web and mobile-phone connectivity and to ensure that all operations performed optimally in real-time. At the start of the study, each mobile-phone was authenticated by a two-step process using an automated Short Message Service (SMS) verification code sent to the caregiver's mobile-phone during enrollment. The authenticated mobile-phone would receive a welcome message which was verified by the field worker. For the group receiving compliance-linked incentives, an additional authenticated step was utilized to ensure that mobile-phone on different carriers could receive automated incentives. The field worker identified the carrier by inspecting the mobile-phone screen or the SIM card and entering this information into the software platform. This immediately triggered delivery of mobile-phone talk-time equivalent to Indian Rupee (INR) 20 (~USD 0.33) to the caregiver's mobile-phone, which was then manually verified by the field worker. INR 30 (~USD 0.50) per completed immunization was provided subsequently to this group. Pre-scripted instructions were verbally provided at recruitment and at each follow up visit as follows: caregivers of children assigned to the control group were informed to come back for immunization at the next scheduled date, caregivers of children assigned to automated mobile-phone reminders alone were informed to come back for immunization on the date indicated by the automated mobile-phone reminder and caregivers of children assigned to automated reminders with compliance-linked incentives were informed to come back for immunization on the date indicated by the automated mobile-phone reminder, and that they would receive a specified amount of mobile-phone talk-time at the follow up visit.

*Biometric identification:* Biometric information (right index finger print) for the caregiver was collected at enrollment and verified by scanning the same finger seven times. In rare cases where the right index finger was not reliable, the right thumb, left index finger or left thumb was used in that order. Additional caregivers could be added during follow up visits and mobile numbers for caregivers could also be updated, but these procedures required the same verification process as described earlier.

*Automated reminders and compliance-linked incentives:* For the study groups receiving automated reminders, SMS messages in the local language (Hindi) comprising the name of the child and the return date for the next scheduled immunization visit were sent. For the group receiving compliance-linked incentives an SMS message in Hindi stating that mobile-phone talk-time [in Indian Rupee (INR)] would be received on successful completion of the scheduled visit was sent simultaneously with the automated reminder. SMS messages were sent at 8:00 AM Indian Standard Time two days before and on the scheduled day of the immunization and messages were no longer than two sentences. For children who did not return on or before the scheduled date, two additional automated SMS reminders were sent the day after and seven days after the scheduled return date. At follow up visits, mobile-phone minutes equivalent to INR 30 (~USD 0.5) per completed immunization were provided in the compliance-linked incentives group. Immunizations received by a subject elsewhere during the study could also be added to the immunization records for both study groups and the control group, but compliance-linked incentives were only provided for immunizations registered by the software platform in the appropriate study group. Automated reminders were sent to all verified caregivers for a given child, but compliance-linked incentives were only provided to the primary caregiver's mobile-phone (identified during enrollment). All data transfers and compliance-linked incentives transactions were automated and occurred in real-time. We also calculated the cost in mobile-phone messaging and compliance-linked incentives. Since automated reminders were sent to multiple verified caregivers for each child, the costs for mobile-phone messaging (USD 0.0048 per message) was a cumulative of all messages send to all caregivers. However, compliance-linked incentives were only provided to the primary caregiver's mobile-phone and these costs were also included.

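### Timeliness appears to be scored only among doses that were given, so the arm comparison depends on receipt, which the interventions aim to change

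*Combined protocol and SAP*

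**What the plan says.** The End Points section defines two proportions. For coverage, the primary outcome, the number of doses received is "divided by the total number of immunizations required at the time of measurement", so a missed dose lowers the figure. Timeliness, a secondary outcome, is "defined as the proportion of immunizations administered before or within 14 days after the scheduled date recorded during the study", with no separate denominator of due or scheduled doses.

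Study Procedures describes how dates and doses are joined: "Each follow up visit was also correlated with the scheduled return date (if recorded in the system) of the administered immunization". It also says that government staff supplied the date of the next visit at each follow-up and that field workers entered it in the platform.

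The Statistical Analysis Plan adds one sentence: "Comparison between groups for timeliness of immunization was calculated using the Fisher-exact test". It does not say what makes up the rows and columns of that table.

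Two features of the interventions bear on who receives a dose. In the paragraph on automated reminders, for children who had missed the date, "two additional automated SMS reminders were sent the day after and seven days after the scheduled return date"; this applies to the reminder arms only. In the paragraph on authentication, "INR 30 (~USD 0.50) per completed immunization was provided subsequently to this group"; that sentence sets no condition on timing.

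**The concern.** If timeliness is computed among doses given, a child who has a return date and never comes back adds nothing to numerator or denominator, although no dose is less timely. Whether a dose is given is decided after randomisation and is what the reminders and incentives are meant to influence. The arms would then be compared on sets of doses that may differ in kind, and randomisation no longer protects the comparison. An arm that brings in more children, some of them late, can show a lower percentage even with more on-time doses. An arm with many complete defaulters can look good because they are not counted. Taken alone, the secondary result could hide a real gain in timeliness or report it as a loss.

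**Working it through.** **Inputs.** The 14-day window and the outcome wording come from End Points, and the link between date and dose from Study Procedures. The documents give no timeliness figure to reproduce; the 175 per group in the Statistical Analysis Plan concerns coverage. They also give no coverage or timeliness percentages, so every count below is an assumption.

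**Step 1: the two measures.** For one arm, let D be doses with a recorded scheduled date, G those given at any time, and T those given by day 14.

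- Administered measure: A = T/G
- Dated measure: B = T/D
- Receipt: R = G/D, so A = B/R

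For intervention (I) against control (C), A_I/A_C = (B_I/B_C) ÷ (R_I/R_C).

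On the ratio scale, the administered measure marks down whichever arm has the higher receipt of its dated doses.

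**Step 2: numbers.** Each arm column shows T/G; differences are intervention minus control, in percentage points.

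| D per arm | Control | Intervention | Administered measure | Dated measure |
|---|---|---|---|---|
| 100 | 40/50 | 50/70 | 80% vs 71.4% (−8.6) | 40% vs 50% (+10) |
| 100 | 40/50 | 60/60 | 80% vs 100% (+20) | 40% vs 60% (+20) |
| 100 | 40/50 | 55/55 | 80% vs 100% (+20) | 40% vs 55% (+15) |
| 100 | 40/50 | 45/50 | 80% vs 90% (+10) | 40% vs 45% (+5) |
| 500 | 150/200 | 150/300 | 75% vs 50% (−25) | 30% vs 30% (0) |
| 500 | 150/200 | 150/225 | 75% vs 66.7% (−8.3) | 30% vs 30% (0) |
| 500 | 150/200 | 200/350 | 75% vs 57.1% (−17.9) | 30% vs 40% (+10) |
| 500 | 150/200 | 225/300 | 75% vs 75% (0) | 30% vs 45% (+15) |

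Check of the first row against Step 1: B_I/B_C = 50/40 = 1.25 and R_I/R_C = 0.70/0.50 = 1.40, so A_I/A_C = 1.25/1.40 = 0.893, which equals 71.4/80.

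**Step 3: Fisher's exact test on the 500-dose rows**, treating doses as independent.

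| Intervention | p, administered | p, dated |
|---|---|---|
| 150/300 | about 2×10⁻⁸ (against intervention) | 1.0 |
| 150/225 | about 0.07 | 1.0 |
| 200/350 | about 3×10⁻⁵ (against intervention) | about 0.001 (for intervention) |
| 225/300 | 1.0 | about 1×10⁻⁶ (for intervention) |

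The choice of denominator can create, hide or reverse a difference. In percentage points it can also leave a difference unchanged (60/60) or enlarge it (55/55 and 45/50).

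**Step 4: possible scale in this trial.** The plan expects its best intervention to "increase the baseline immunization coverage by least 20% compared to the control group", without saying whether this is relative or absolute. Suppose the gain carries over to dated doses. If relative, R_I/R_C = 1.20, and the intervention arm needs 20% more on-time doses to show equal timeliness. If it is 20 points on an assumed baseline of 40%, R_I/R_C = 60/40 = 1.50, and it needs 50% more.

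**The case against.** **The denominator is inferred.** The definition can be read as the share, among doses with a recorded date, that were given by day 14. On that reading doses never given already count as untimely. The sentence in Study Procedures concerns data linkage and does not define the outcome. This stands as a limit on certainty. The administered-dose reading is still the likelier one, because only coverage is given a denominator of required doses and because the date is attached to a dose that was given. If the other reading was meant, the text must say so, since two analysts could report opposite results.

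**The direction is not fixed.** A reader might infer that the measure is bound to work against the reminder arms because the extra messages bring in late children. The documents do not support that. Messages on day 1 and day 7 after the missed date both fall inside the 14-day window, the second with 7 days left, so a child who responds promptly is scored timely. Nor does any section say that comparable children in the control arm stay unvaccinated; they may come after day 14 and count as late.

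**Distortion is not tied to coverage in a simple way.** A reader might also infer that the distortion vanishes only when the intervention leaves coverage unchanged. The 60/60 row refutes this: receipt differs by 10 points and both measures give +20. The 45/50 row shows the converse, with equal receipt and different gaps in points.

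**Missed doses are counted elsewhere.** This is correct. Coverage penalises them, so the primary outcome is untouched and timeliness among doses given is a legitimate description.

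**Dated doses are not a clean denominator either.** This also stands. The next date is supplied at each follow-up, so children who return accumulate more dates and a permanent defaulter does not. Changing the denominator removes the main selection but not all of it.

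**Conclusion.** The concern holds in a limited form. On its most natural reading, the plan scores timeliness among administered doses with a recorded date, and nothing in it says that a dated dose never given is untimely. The Fisher comparison then conditions on a post-randomisation event that the interventions target, and it can mislead in either direction. With assumed counts, a gain of 10 points on dated doses appears as a loss of about 9 points on administered doses, and a gain of 15 points can disappear. These figures show what is possible; they do not estimate the effect in this trial, for which the documents give no data. The conclusion rests on the administered-dose reading and on receipt of dated doses differing between arms. It is confined to the secondary outcome and should be corrected, but it does not threaten the primary analysis.

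**What to change.** In End Points, define timeliness as doses given on or before day 14 after the recorded scheduled date, divided by all doses with a recorded scheduled date at least 14 days before the end of follow-up. Count doses given later, or never, as not timely. Make this the denominator of the test in the Statistical Analysis Plan.

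Because later dates go only to children who return, add an analysis restricted to each child's first scheduled date recorded after randomisation. Each child with a recorded date then contributes regardless of later attendance. Report by arm how many children have no such date.

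State how doses with no recorded date and doses received elsewhere are handled. Keep the proportion among administered doses as a descriptive figure.

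The cost is a change of wording and a little more analysis from dates already in the platform, with no new data collection. Reported timeliness will be lower in any arm with dated doses that were never given. The text is written in the past tense, so if results were known when the change is made, the new analysis should be labelled accordingly.

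### Timeliness is a delay in days cut at day 14 and tested on immunizations with Fisher's exact test, which loses power under smooth delay shifts and ignores clustering of doses within a child

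*Combined protocol and SAP*

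**What the plan says.** End Points makes timeliness a secondary outcome, "defined as the proportion of immunizations administered before or within 14 days after the scheduled date recorded during the study". The thing counted is the immunization, so one child can contribute several observations. The Statistical Analysis Plan names one method for it: "Comparison between groups for timeliness of immunization was calculated using the Fisher-exact test".

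Study Procedures shows what is held. On the scheduled date: "The date for the next scheduled immunization visit was provided at each follow up by the government staff and entered into the software platform". On the link to the visit: "Each follow up visit was also correlated with the scheduled return date (if recorded in the system) of the administered immunization". A delay in days can therefore be computed for every administered dose that has a recorded scheduled date. A dose without one cannot be classified as timely either, so both analyses draw on the same doses.

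Under End Points, the paragraph on automated reminders sends messages two days before and on the scheduled day; for children who have not come, "two additional automated SMS reminders were sent the day after and seven days after the scheduled return date". The documents give no reason for choosing 14 days, no analysis of the delay itself, and no expected timely share, effect or power for this outcome.

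**The concern.** Two features of the analysis work against it.

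**The cut.** Messages go out on days -2, 0, +1 and +7, so the intended effect is a return close to the scheduled date. A visit brought forward from day 12 to day 1 scores nothing. Nor does one brought forward from day 60 to day 20. If reminders or incentives shift the whole delay distribution, the yes/no outcome sees only what crosses day 14, and a real gain could be reported as no effect.

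**The unit.** Fisher's exact test assumes independent observations. Doses from the same child share a caregiver, a household and a distance to the clinic. Counting them as independent makes the evidence look stronger than it is, so a chance difference could be reported as an effect.

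The two errors pull in opposite directions, which makes the planned p-value hard to interpret either way.

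**Working it through.** **Inputs.** From the Statistical Analysis Plan: "a sample of size 175 per group would yield us 90% power at 5% level of significance for this outcome", an effect stated as "we anticipated that our best intervention would increase the baseline immunization coverage by least 20% compared to the control group", and "Assuming up to a 20% exclusion rate". Everything about timeliness below (rates, delay shape, doses per child, ICC, two-sided testing) is assumed.

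**1. The plan's own figure.** For two proportions, n = [1.960·√(2p̄q̄) + 1.282·√(p₁q₁ + p₂q₂)]² / d². With 40% v 60% (baseline assumed, none is given), n = (1.386 + 0.888)² / 0.04 = 129.3. The continuity correction (n/4)(1 + √(1 + 4/(n·d)))² gives 139.1, so 140, and 140/0.8 = 175. The stated size reproduces, but it is for coverage. It supplies only the 140 evaluable children per arm used below.

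**2. One dose per child, smooth shift.** Exponential delays with rate λ = -ln(1 - p)/14 give a timely share p at day 14. Lognormal delays (SD of log 1.2) were shifted to the same shares. Delays were capped at 90 days, with 2000 replicates (Monte Carlo standard error at most √(0.25/2000) = 1.1 points).

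| Timely share | Delays | Fisher | Rank test on days | Difference (points) |
|---|---|---|---|---|
| 30% v 40% | exponential | 38.3% | 71.6% | 33.3 |
| 50% v 65% | exponential | 65.9% | 83.9% | 18.0 |
| 50% v 65% | lognormal | 66.7% | 87.1% | 20.4 |
| 70% v 85% | exponential | 83.3% | 90.7% | 7.4 |

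Hand check for 50% v 65%: λ is 0.0495 v 0.0750 per day, so median delay is 14.0 v 9.2 days. The chance that a treated child comes sooner is 0.0750/(0.0495 + 0.0750) = 0.602. The null standard error is √(281/(12·140²)) = 0.0346. Power ≈ Φ(0.102/0.0346 - 1.96) ≈ Φ(1.0) = 84%, as simulated.

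Not all of the gap is due to the cut. Exact power for 50% v 65% is 67% with Fisher and 71% with an uncorrected chi-square test; for 70% v 80% it is 44% v 49%. About 4 to 5 points come from Fisher's discreteness. Over a wider set of smooth shapes and rates, at 140 or 175 per arm, the loss ran from about 3 to 72 points, so 7 to 33 is one plausible range.

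**3. Several doses per child.** 140 children per arm, exponential delays, ICC 0.3 on the underlying delay scale. Each cell is Fisher on doses v rank test on child means.

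| Timely share | 3 doses | 5 doses |
|---|---|---|
| 50% v 65% | 98% v 99% | 99.7% v 99.8% |
| 50% v 60% | 77% v 85% | 90% v 92% |
| 30% v 40% | 81% v 97% | 93% v 99% |

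Fisher does not hold its 5% level here (step 4), so this is not a fair comparison. The fair one is against a child-level test of the proportion timely. The rank test's gain over that was 3 points (50% v 65%, 3 doses), 12 to 16 points (50% v 60%) and 16 to 23 points (30% v 40%). A repeat at these settings put the overall range at about 1 to 22.

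**4. Type I error of Fisher on doses.** At a 50% timely share, an ICC of 0.3 on the delay scale corresponds to (2/π)·arcsin(0.3) = 0.194 on the yes/no scale. The design effect 1 + (m - 1)·0.194 is 1.39 at 3 doses and 1.78 at 5. The true level of a nominal 5% test is then 2[1 - Φ(1.96/√1.39)] = 9.6% and 2[1 - Φ(1.96/√1.78)], about 14%. Simulations gave about 7-15% at ICC 0.3, and about 6-19% over ICC 0.1 to 0.5. A rank test on doses would also fail (8-26%). A rank test on child means, with 1 to 5 doses per child, stayed at 3.8-5.1%.

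**5. Effects that are not smooth (one observation per child).**
- Effect only in days 0-14, same hazard afterwards: rank v Fisher 62% v 70%, 68% v 67% and 88% v 83% at control shares of 30%, 50% and 70%.
- Late doses only moved inside the window: the rank test is about 9 to 54 points worse.

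**6. Doses never given.** With 20% per arm never immunized and ranked last, rank v Fisher was 75% v 69% and 68% v 68% at control shares of 30% and 50%. If only observed delays are used, turning never-returners into late returners looks harmful: with 50% timely in both arms and 20% v 35% late, the test was significant in the wrong direction in 36% of runs.

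**The case against.** The strongest defence is that the percentage given on time is a familiar programme measure, that timeliness is secondary and unpowered, and that the advantage of a delay analysis is not guaranteed. Every reminder falls within days -2 to +7. An effect that mainly pulls late doses just inside the window is possible, and the binary outcome would then be the better one. This stands as a limit on the size of the gain and as a reason to keep the 14-day figure. It does not justify making that figure the only comparison: no message is sent at or near day 14, and nothing in the documents makes a threshold effect the expected pattern.

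Three stronger readings are tempting and not supported:

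- A reader might take 7 to 33 points as the loss in this trial. It holds for one dose per child under assumed rates and smooth shifts; End Points counts immunizations.
- A reader might think Fisher's test is merely conservative. At one dose per child it is (simulated level 2.9%, against 4.1% for the rank test). With several doses per child this reverses.
- A reader might infer that a delay exists for every dose. Study Procedures limits the link to recorded scheduled dates, and a dose never given has no administration date.

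One caveat runs the other way. The plan does not say outright that Fisher's test is applied to doses; that follows from the outcome definition. If each child contributed one dose, the clustering problem disappears and step 2 is the relevant comparison.

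**Conclusion.** The point holds, in a bounded form. The plan replaces an available delay in days with a 14-day indicator and, on the natural reading, tests it as if doses within a child were independent. Under smooth shifts with 140 children per arm and exponential delays, a child-level rank test gains about 7 to 33 points over Fisher at one dose per child. At 3 to 5 doses and ICC 0.3, it gains about 1 to 22 points over a valid child-level test of the proportion. There may be no gain, or a loss, if the effect acts only around day 14. The anti-conservative level of about 7-15% at 3 to 5 doses matters at least as much as the lost power. All rates, dose counts and ICCs are assumptions. The consequence is confined to a secondary outcome; the sample size and the primary comparison are untouched by this point.

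**What to change.** Change the timeliness sentences in End Points and the Statistical Analysis Plan so that the between-group test is a child-level comparison of days from scheduled date to administration. Either form would do:

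- a rank test on one value per child, with doses due but not given set to a stated cap (for example 90 days) or ranked last; or
- a time-to-visit analysis from the scheduled date, censored at study end, with standard errors clustered by child.

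State which doses enter (those with a recorded scheduled date) and how many are left out in each group. Keep the proportion within 14 days as the descriptive summary, with a confidence interval that allows for clustering by child.

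The cost is a few sentences and a few lines of Stata code, with no new data or participants. A difference in days is less familiar than percent on time, and power may be lower if the effect is confined to the 14-day threshold. The text is written in the past tense, so if the change is made after unblinding, the new analysis should be labelled as such and shown beside the planned one.
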